- Algorithm 1 (paper algorithm): dose adjustment guidance provided (Section 10.8); study participant will receive an initial individualized LY3209590 dose on Day 1 with weekly adjustments based on fasting glucose (FG) and hypoglycemia data for the first 12 weeks, then every 4 weeks.

For patients randomized to LY3209590 Algorithm 1, documented guidance for dose adjustment is provided (Section 10.8).

For patients randomized to the insulin degludec arm the following guidance for administration is applicable:

Insulin degludec will be self-administered daily by participants after a training and first administration under site personnel supervision on Day 1 according to a modified Riddle algorithm (Section 10.8).

General considerations

Study procedures will be performed as listed in the Schedule of Activities (Section 1.3).

To allow timely sampling for PK assessments, visits for collection of the samples will be scheduled within the required time windows provided in the Schedule of Activities.

Participants will continue to use concomitant metformin (alone or in combination with a stable dose of a DPP4V inhibitor and / or a SGLT2 inhibitor) throughout the treatment period. Discontinuation or changes to dose are not permitted, except in situations where dose adjustment or complete discontinuation is required per country-specific label or when allowed per study protocol (for further details, see Section 6.5.2).

Self Monitoring of Blood Glucose (SMBG): All measurements have to be recorded in the provided electronic diary. Participants will be instructed to perform FG measurements each day. In addition, two 6-point SMBG profiles (prior to and 2 hours after the morning, midday, and evening meals) should be done on nonconsecutive days in the week prior to the required visits noted in the Schedule of Activities (Section 1.3).

Participants who develop severe, persistent hyperglycemia based on prespecified thresholds (see Section 6.1.2.3) will receive a new glucose-lowering intervention (or rescue therapy) based on clinical judgment of the investigator (see table in Section 6.5). Participants who need rescue therapy will continue on IP in the trial until they complete all study visits.

Flash glucose monitoring (FGM): Participants will undergo 3 FGM sessions using the LibrePro System (Abbott) in the 14-day period prior to randomization, Visit 15, and Visit 20. Patients will remain blinded to these assessments until the study is completed.

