9.4.3. Primary endpoint(s)

The primary objective is to compare the HbA1c change from baseline to Week 26 between LY3209590 treatment and insulin degludec. It is intended to estimate the treatment differences in the change in HbA1c from baseline to 26 weeks if participants adhered to the treatment without intercurrent events (stop of the study medication and/or use of rescue medication). It is a type of hypothetical estimand based on International Council for Harmonisation (ICH) E9(R1). Only data before the occurrence of the intercurrent events (use of rescue medication or stop of the study medication) will be included in the analysis and the resulting missing values will be imputed implicitly in the mixed-effect model for repeated measurements (MMRM) analysis. The MMRM model will include treatment, strata (country, DPPIV [yes/no], SGLT2 [yes/no] and baseline BMI [<30 , ≥ 30]), visit, and treatment by visit interaction as fixed factors and the baseline of the dependent variable as a continuous covariate.

As a sensitivity analysis, the treatment differences in HbA1c change from baseline to Week 26, only if patients could complete the treatment, will also be estimated. More details will be specified in the SAP.

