- Replacing the 2-step imputation method with return to baseline imputation for the supportive estimand
- Replacing the longitudinal logistic regression with logistic regression based on multiple imputation for the HbA1c target analyses
- Adding potential sensitivity analysis which will censor the data from patients who significantly deviated from the study dose algorithm
- Adding sensitivity analysis for the comparison between pooled LY3209590 group and insulin degludec
- Deleting the t-test for exposure comparison
- Adding the adjudication details for nonfatal cardiovascular events
- Adding details for analyses (for example, analysis models for different types of flash glucose monitoring [FGM]-derived variables, analysis population)
- Clarifying that the study team is unblinded to the study treatment for patient safety monitoring
- Updating the analyses for hypoglycemia event rates from negative binomial regression to empirical method
- Adding one more subgroup for analyses: Concomitant medication (metformin alone and metformin in combination with other allowed oral antidiabetic medications)
- Updating the subgroup analyses for documented, nocturnal, and non-nocturnal hypoglycemia rates (defined by glucose <70 mg/dL [3.9 mmol/L] and glucose \geq 54 mg/dL [3.0 mmol/L]) during 0-26 weeks.

4. Study Objectives

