5.1. General Considerations

All data will be entered, verified, and archived at a contract research organization (CRO) external to Eli Lilly and Company (Lilly) and/or at Lilly. Data listings, summaries, and analyses will be performed by a CRO and/or by Lilly under the guidance and approval of statisticians at Lilly.

Statistical analysis of this study will be the responsibility of sponsor or its designee. Any change to the data analysis methods described in the protocol will require an amendment only if it changes a principal feature of the protocol. Any other change to the data analysis methods described in the protocol, and the justification for making the change, will be described in this SAP and/or the clinical study report (CSR). Additional exploratory analyses of the data will be conducted as deemed appropriate.

The following populations are defined for purpose of analysis:

Population	Description
Entered/Enrolled Population	All participants who sign the ICF
Randomized Population	All participants assigned to treatment, regardless of whether they take any doses of study treatment, or if they took the correct treatment. The participants previously randomized to LY3209590 Algorithm 2 will be pooled with the participants randomized to Algorithm 1 and all of these participants will be analyzed as one treatment group of LY3209590.
Efficacy Population	All participants randomized to either LY3209590 Algorithm 1 or insulin degludec and took at least 1 dose of study treatment. Participants will be analyzed according to the treatment they were assigned.
Safety Population	All participants randomly assigned to study treatment and who took at least 1 dose of study treatment. The participants previously randomized to LY3209590 Algorithm 2 will be pooled with the participants randomized to Algorithm 1 and all of these participants will be analyzed as one treatment group of LY3209590.
Pharmacokinetic Population	All randomized participants who received at least 1 dose of LY3209590 and have at least 1 evaluable PK sample.

Abbreviations: ICF = informed consent form; PK = pharmacokinetics.

Unless otherwise stated, the efficacy analyses will be conducted on efficacy analyses set (EAS) based on Efficacy Population using the data up to the study treatment discontinuation (defined as

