the observed data with collection date before or on the last dose date +10 days). Sensitivity analyses for selected efficacy measures may be conducted on the Randomized Population using the data up to the study treatment discontinuation.

Unless otherwise stated, the safety analyses will be conducted on the safety analyses set based on the Safety Population using all data collected during the study including treatment and follow-up periods regardless of the treatment disposition status. The safety measures will be summarized and compared between LY3209590 (by pooling LY3209590 Algorithm 1 and LY3209590 Algorithm 2 data) and insulin degludec. Safety parameters derived from FGM measures will be summarized and compared between LY3209590 Algorithm 1 and insulin degludec.

Unless otherwise specified, the baseline value used for the analyses will be the last non-missing value obtained for each participant prior to or on the date of first study IP dose (or randomization visit date if first dose date is missing). The baseline liver enzyme lab measures will be the average of all assessments prior to and at randomization visit.

All tests of treatment effects will be conducted at a 2-sided alpha level of 0.1, unless otherwise stated, and all confidence intervals (CIs) will be given at a 2-sided 90% level.

Puerto Rico and the United States (US) are always pooled in the analysis, as Puerto Rico will be considered part of US during randomization. All analyses using country in the model will use pooled country, unless otherwise specified. No other pooling of countries is needed.

For continuous measurements, summary statistics will include sample size, mean, median, standard deviation (SD), minimum, and maximum. For certain variables that are considered to be log-normally distributed, the geometric mean and coefficient of variation (CV) will be provided instead.

For categorical measurements, summary statistics will include sample size, frequency, and percentage. Fisher's exact test will be used. Chi-squared test will be used for multi-category variables.

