5.7. Primary Outcome and Methodology

The primary objective is to compare the HbA1c change from baseline to Week 26 between LY3209590 and insulin degludec and will be based on the primary estimand described below.

The primary estimand is the treatment differences in the change in HbA1c from baseline to 26 weeks for the targeted study population if all patients would adhere to the treatment without intercurrent events. The analysis data will include data up to the discontinuation of study treatment for the Efficacy Population with baseline and at least one non-missing postbaseline measurement. There may be missing values due to the early discontinuation of study treatment. The MMRM model will be used with the HbA1c changes at Week 6, 12, 16 and 26 (the primary endpoint) and the missing values will be imputed implicitly in the MMRM analysis under the assumption of missing at random. The MMRM model will include treatment (LY3209590 Algorithm 1, insulin degludec), strata (country, DPPIV [yes/no], SGLT2 [yes/no] and baseline BMI [<30 , ≥ 30]), visit, and treatment by visit interaction and the baseline value of the dependent

variable as the fixed effects. The HbA1c is reported in unit of % and will be converted to the unit of mmol/mol using the following formula: HbA1c in mmol/mol = 10.93*HbA1c in % - 23.5 (<http://www.ngsp.org/ifccngsp.asp>). HbA1c analysis will be conducted based on both units.

In the MMRM model, the within-patient errors are modeled as an unstructured variance-covariance matrix. If the analysis fails to converge, the following variance-covariance matrix will be used (in order) until one converges:

1. Toeplitz with heterogeneity
2. autoregressive with heterogeneity
3. compound symmetry with heterogeneous variances
4. Toeplitz
5. autoregressive
6. compound symmetry without heterogeneous variances

The Kenward-Roger approximation will be used to estimate denominator degrees of freedom for the MMRM models. The following is an example SAS code:

```
proc mixed data=DATA;  
  class TREATMENT STRATIFICATIONS VISIT PATIENT;  
  model HbA1c=BASELINE TREATMENT STRATIFICATIONS VISIT  
        VISIT*TREATMENT / solution ddfm=kr;  
  repeated VISIT / subject=PATIENT type=un;  
  lsmeans TREATMENT*VISIT/ pdiff cl alpha=0.1 om=DATA;  
run;
```

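### The SAP's primary HbA1c data rule cuts only at treatment discontinuation, so read literally it keeps post-rescue values that the protocol's estimand excludes

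*SAP*

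**What the plan says.** Protocol 9.4.3 sets a hypothetical estimand for HbA1c change to Week 26. It names two intercurrent events and attaches a data rule: "Only data before the occurrence of the intercurrent events (use of rescue medication or stop of the study medication) will be included in the analysis". The values removed in this way are left to the MMRM.

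SAP 5.7 targets the same kind of effect but does not say what the intercurrent events are. Its data rule is "The analysis data will include data up to the discontinuation of study treatment for the Efficacy Population". The one source of missing values it names is discontinuation: "There may be missing values due to the early discontinuation of study treatment". SAP 5.1 makes the cut operational as "the observed data with collection date before or on the last dose date +10 days". The SAP mentions rescue only in the supportive estimand, which applies whether or not rescue was used.

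On conduct, Protocol 4.1.1 says: "Participants who need rescue therapy will continue on IP in the trial until they complete all study visits". Protocol 6.1.2.3 agrees. Protocol 7.2 says something different: a participant who needs another effective agent leaves the study before that agent is started.

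**The concern.** Starting rescue does not stop study drug, so it does not trigger the SAP's cut. A programmer who follows SAP 5.7 and 5.1 as written would keep HbA1c measured after rescue. One who goes back to Protocol 9.4.3 would set it to missing. The SAP does not settle which dataset is primary.

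That dataset feeds the only non-inferiority decision: upper limit of the two-sided 90% CI below +0.4%. No other SAP analysis is stated to remove post-rescue HbA1c, and the supportive estimand keeps it by design. Under the literal rule, the protocol's primary estimand would therefore not be estimated anywhere. The trial is open-label and SAP 6 leaves the study team unblinded, so this choice should be fixed in writing beforehand.

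**Working it through.** **1. The two rules side by side**

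| | Protocol 9.4.3 | SAP 5.7 with 5.1 |
|---|---|---|
| Intercurrent events | Rescue; stopping study drug | Referred to, not defined |
| Data admitted | Before either event | Up to last dose +10 days |
| HbA1c after rescue, on study drug | Excluded | Kept |

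Protocol 9.4.1 has the same general +10 days cut, but only where nothing else is stated, and 9.4.3 states a stricter rule.

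**2. The plan's own figure**

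Inputs from Protocol 9.2: SD 1.1, 100 completers per arm, margin 0.4, true difference 0, two-sided alpha 0.1.

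- SE = 1.1 × √(2/100) = 0.1556.
- Power = Φ(0.4/0.1556 − 1.645) = 82.3%, which agrees with the stated figure of more than 80%.
- 250 × 0.80 = 200 completers.

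The sample size is not affected by this point.

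**3. Effect of keeping post-rescue HbA1c**

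The documents give no rescue rate or rescue effect, so both are assumed. Let e be the fall in Week 26 HbA1c due to rescue (0.5 to 1.0 points) and p the share rescued in each arm. The difference moves in favour of LY3209590 by b = (p_LY − p_deg) × e. With a true difference of 0.4, the one-sided error is Φ(b/SE − 1.645).

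| Excess rescue on LY3209590 | e = 0.5 | e = 1.0 |
|---|---|---|
| −2 points | 4.4% | 3.8% |
| 0 | 5.0% | 5.0% |
| +1 point | 5.3% | 5.7% |
| +2 points | 5.7% | 6.5% |

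**4. If one HbA1c-linked trigger acts in both arms**

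When LY3209590 is truly worse by 0.4, the same threshold rescues more of its participants: p_LY = 1 − Φ(z(1 − p_deg) − 0.4/1.1).

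| p_deg | p_LY | Error, e = 0.5 to 1.0 |
|---|---|---|
| 0.5% | 1.35% | 5.3–5.6% |
| 1% | 2.48% | 5.5–6.1% |
| 2% | 4.55% | 5.9–6.9% |
| 5% | 10.01% | 6.9–9.3% |

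At the margin, a common trigger therefore pushes in the lenient direction.

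**5. Does the protocol's cut restore 5%?**

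This was simulated with 2,000,000 per arm, visits at Weeks 6, 12, 16 and 26, an assumed within-patient correlation of 0.7, and one fasting-glucose threshold applied after Weeks 12 and 16.

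- Case A: fasting glucose depends only on current HbA1c (r 0.7 to 0.9, degludec rescue 1 to 5%). Keeping the data gives 5.35–9.00%; cutting gives 4.99–5.01%.
- Case B: fasting glucose also predicts Week 26 HbA1c with correlation r. Missing at random then fails for an MMRM without glucose:

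| r | p_deg | Kept, e = 0.5 | Kept, e = 1.0 | Cut | Cut + fasting glucose |
|---|---|---|---|---|---|
| 0.7 | 1% | 5.33% | 5.68% | 5.52% | 4.99% |
| 0.7 | 2% | 5.60% | 6.25% | 5.88% | 5.00% |
| 0.7 | 5% | 6.27% | 7.79% | 6.68% | 4.99% |
| 0.9 | 1% | 5.44% | 5.91% | 5.89% | 5.00% |
| 0.9 | 2% | 5.81% | 6.71% | 6.52% | 5.00% |
| 0.9 | 5% | 6.69% | 8.80% | 8.02% | 5.00% |

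In case B, cutting is worse than keeping in all six settings when e = 0.5 and better in all six when e = 1.0. The cut with pre-rescue fasting glucose in the imputation model stays at 5.0% throughout.

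**The case against.** The intended rule can largely be recovered. The protocol calls the SAP a fuller account of its analyses, not a replacement. The term that SAP 5.7 leaves undefined is defined in Protocol 9.4.3. The supportive estimand, which ignores rescue, implies that the primary one does not. The SAP's sentence on missing values need not be exhaustive. All this makes it likely that exclusion was intended, but the operative sentence still does not apply it.

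A deliberate change is unlikely but cannot be ruled out from the text. SAP 5.1 commits that "Any other change to the data analysis methods described in the protocol, and the justification for making the change, will be described in this SAP" or in the study report, and SAP 5.7 describes no such change. The revision history adds little. Its only item that names an estimand is "Replacing the 2-step imputation method with return to baseline imputation for the supportive estimand", and it compares two SAP versions, not the SAP with the protocol.

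The effect may also be near zero. Rescue requires average fasting glucose above 270, 240 or 200 mg/dL (depending on the study week) over at least 2 weeks, while both arms titrate to 100 mg/dL or below and entry HbA1c is capped at 9.5%. If Protocol 7.2 governs, little or no post-rescue HbA1c would exist. The closed-form figures give each rescued participant the full effect by Week 26, so they lean high. These points stand, and they limit what can be claimed about size.

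Finally, the cut is not a reliable remedy for error. In case B with e = 0.5, r = 0.9 and 2% rescue, the excess over 5% is 1.52 points when cut against 0.81 when kept. This also stands. The case for the cut is that it matches the stated estimand.

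**Conclusion.** The concern holds. SAP 5.7 leaves the intercurrent events undefined, and its stated data rule admits HbA1c that Protocol 9.4.3 excludes from the primary analysis. This is a wrong data rule for the declared estimand, in the analysis that decides non-inferiority, and it must be corrected before database lock.

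Confidence is high on the textual mismatch. The numerical consequence is undetermined: its direction follows the rescue imbalance, and rare rescue means a small effect. All error figures rest on assumed rescue rates, rescue effects and correlations.

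**What to change.** In SAP 5.7:

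- Define the intercurrent events as in Protocol 9.4.3: use of rescue medication and stopping study drug.
- For the primary MMRM, set to missing any HbA1c collected after the first rescue date or after last dose +10 days, whichever is earlier. Keep the +10 days: the last LY3209590 dose is at Week 25, so a Week 26 visit at the end of its ±3-day window falls 7 + 3 = 10 days after it.
- Distinguish rescue from acute insulin use of up to 14 days, using the recorded dates and reasons for use.
- Report rescue counts by arm.
- Optionally, add a sensitivity analysis that multiply imputes post-rescue HbA1c with pre-rescue fasting glucose as an auxiliary variable. The trigger is fasting glucose, which the MMRM omits, and the data exist: "Participants will be instructed to perform FG measurements each day".

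Separately, Protocol 7.2 must be reconciled with 4.1.1 and 6.1.2.3 on participants who need another agent.

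The cost is a few sentences and one censoring flag built from data already collected (dates and reasons under Protocol 6.5, dose increases of oral agents under 6.5.2). The downside is slightly more missing data and more reliance on missing at random. In a finite-sample check (4,000 trials, 100 per arm, case A with r = 0.7), the SD of the estimate rose by 0.6% at 2% degludec rescue and by 1.7% at 5%.

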5.8. Secondary and Additional Efficacy Analyses

The primary population for the secondary analysis on HbA1c reduction is the EAS. Treatment comparison at 26 weeks will be used to assess the differences. The 2-sided 90% CI for the LS mean of the differences in the change in HbA1c at 26 weeks will also be constructed.

The following secondary efficacy outcomes will be analyzed based on the EAS using the same MMRM model as the primary analysis with the addition term of HbA1c strata (<8.5% and \geq 8.5%) for non-HbA1c measures:

1. HbA1c change from baseline to Week 12.
2. Fasting blood glucose (FBG) and change by SMBG from baseline to Week 12 and Week 26;
3. Fasting serum glucose (FSG) by laboratory and change from baseline at Weeks 12 and 26;
4. Between-day glucose variability measured by the SD and the CV of the FBG at Week 12 and 26;
5. Six-point SMBG profile (pre-meal and 2-hour postprandial SMBG measurements for the morning, midday, and evening meals) at Weeks 12 and 26.
6. Within-day and between-day glucose variability measured by the SD and the CV of 6-point SMBG.

For the between-day and within-day glucose variability, the variables will take a log-transformation before performing the MMRM analysis.

The proportion of the patients with HbA1c <7.0% (or \leq 6.5%) will be analyzed based on the multiple imputation with the following steps: 1) imputing the missing values in the continuous HbA1c by treatment, 2) dichotomizing the “complete” continuous HbA1c into binary based on the threshold, then 3) fitting the logistic regression model at each scheduled postbaseline visit, and 4) using Rubin’s rule to combine the results. In the logistic regression model, the independent variables of treatment, country, BMI strata (BMI <30 or \geq 30), DPPIV use [yes/no], SGLT2 use [yes/no], baseline HbA1c value will be used.

The above analyses may be repeated to compare LY3209590 (by pooling LY3209590 Algorithm 1 and LY3209590 Algorithm 2) with insulin degludec.

The insulin dose units are different between LY3209590 (mg) and insulin degludec (unit). Therefore, descriptive statistics will be provided for the insulin dose and the dose change from baseline. A loading dose strategy was used only for the first dose of LY3209590. One third of the loading dose will be used as the baseline dose of LY3209590 in the analysis while the dose of insulin degludec at Week 0 will be used as the baseline dose of insulin degludec. No treatment comparison will be conducted. Two sample t-test will be conducted to assess the change from baseline within treatment group.

5.9. Pharmacokinetic/Pharmacodynamic Analyses

Pharmacokinetic/pharmacodynamics (PK/PD) analyses will be conducted by PK/PD group.

5.10. Safety Analyses

Safety measures will include AEs, vital signs, hypoglycemic episodes, treatment exposure, adjudicated cardiovascular events, laboratory measurements, electrocardiograms (ECGs) and immunogenicity. Safety analysis will be reported for the Safety Population using data measured while on treatment and after study drug discontinuation. Unless otherwise specified, the comparison will be between LY3209590 (by pooling LY3209590 Algorithm 1 and LY3209590 Algorithm 2) and insulin degludec.

5.10.1. Study Drug Exposure

Exposure in days in the study will be calculated for each patient and summarized by treatment group. Exposure during the treatment period will be calculated from date of first study basal insulin dose collected in the electronic case report form (eCRF) to date of discontinuation from study treatment (i.e., the last dose date for insulin degludec, and the last dose date + 7 days for LY3209590). The sum of exposure in total patient years will also be provided.

Frequency of subjects falling into the following different exposure ranges will also be summarized: >0 days, ≥ 7 days, ≥ 14 days, ≥ 30 days (1 month), ≥ 60 days (2 months), ≥ 90 days (3 months), ≥ 120 days (4 months), ≥ 183 days (6 months) days.

In addition, the duration of follow-up in days for each individual patient is calculated from the date of last dose of study drug for insulin degludec or the date of last dose of study drug + 7 days for LY3209590 to the last study visit date. The duration of the follow-up in days will be summarized (n, mean, standard deviation, minimum, maximum, median, and sum in total patient years) by treatment group.

The duration on study from date of the first study drug to the last study visit date (including the follow-up visit) will also be summarized by treatment group, the following summary statistics will be provided: n, mean, standard deviation, minimum, maximum, median, and sum in total patient years.

A by-patient listing of drug exposure data will be created to provide data for the CSR.

